7.2 Protocol Deviations

Protocol deviations are captured by the clinical site and provided in the CSR in a similar format to that provided by the clinical site. Protocol deviations are not edited or processed in SAS®.

7.3 Demographics

Descriptive statistics will be calculated for continuous variables (age, body mass index, height, and weight) by randomized treatment sequence and overall. Age will be approximated by subtracting the year of birth from the year of informed consent. If year of informed consent – year of birth is one more than the protocol maximum age then the age approximation will be year of informed consent – year of birth – 1. Descriptive statistics for body mass index, height, and weight will be calculated using screening measurements.

Frequency counts will be provided for categorical variables (sex, race, and ethnicity) for each randomized treatment sequence and overall.

7.4 Adverse Events

All AEs occurring during this clinical trial will be coded using the Medical Dictionary for Regulatory Activities (MedDRA®), Version 25.1.

All AEs captured in the database will be listed in a by-participant data listing including verbatim term, coded term, treatment, onset date/time, resolution date/time, frequency, severity, relationship to study product, relationship to study procedure, and action; however, only TEAEs will be summarized.

A TEAE is defined as an AE that is starting at the time of or after study product administration and within 30 days after the final dose (onset date – last dose date + $1 \le 30$). Each TEAE will be attributed to a treatment based on the onset date and time of the AE compared to that of the respective treatment administration date and time. An AE that occurs during the washout period between treatments will be considered treatment-emergent to the last treatment administered prior to onset of the AE.

If the onset time of an AE is missing and the onset date is the same as the treatment dosing date, then the AE will be considered treatment emergent in the prior and current treatment. If the onset time of an AE is missing and the onset date does not fall on a treatment dosing date, then the AE will be considered treatment emergent for the last treatment administered. If the onset date of an AE is missing, then the AE will be considered treatment emergent and attributed to each treatment on the study, unless the onset date is known to have occurred within or between specific treatment periods.

TEAEs will be tabulated by System Organ Class (SOC) and Preferred Term. Summary tables will include the number of participants reporting the TEAE and as a percent of the number of participants dosed by treatment and overall. The number of TEAEs will be tabulated in a similar manner. A table, which summarizes the number of TEAEs by Preferred Term, severity, and relationship to study product, will also be included.

Serious adverse events (SAEs), if present, will also be listed. Applicable narratives will be included in the CSR.

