9.6 Definitions

9.6.1 AE

An AE is defined as any untoward medical occurrence in a clinical investigation participant administered a drug whether or not considered drug-related (CFR Title 21, Part 312.32(a)); it does not necessarily have to have a causal relationship with this treatment.

An AE can therefore be any unfavorable and unintended sign (e.g., a CS abnormal laboratory finding), symptom, or disease temporally associated with the use of a drug whether or not it is considered related to the drug.

A treatment-emergent adverse event (TEAE) is an AE than begins on or after administration of the first dose of trial medication or an increase in severity or frequency on or after administration of the first dose of trial medication.

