9.6.2 Additional Points to Consider for PTEs and AEs

An untoward finding generally may:

- Indicate a new diagnosis or unexpected worsening of a pre-existing condition. (Intermittent events for pre-existing conditions underlying disease should not be considered AEs)
- Necessitate therapeutic intervention
- Require an invasive diagnostic procedure
- Require discontinuation or a change in dose of study medication or a concomitant medication
- Be considered unfavorable by the investigator for any reason
- AEs caused by a study procedure (e.g., a bruise after blood draw) should be recorded as an AE

Diagnoses vs signs and symptoms:

• Each event should be recorded to represent a single diagnosis. Accompanying signs (including abnormal laboratory values or ECG findings) or symptoms should NOT be recorded as additional AEs. If a diagnosis is unknown, sign(s) or symptom(s) should be recorded appropriately as an AE(s).

Laboratory values and ECG findings:

- Changes in laboratory values or ECG parameters are only considered to be AEs if they are judged to be CS (i.e., if some action or intervention is required or if the Investigator judges the change to be beyond the range of normal physiologic fluctuation). A laboratory re-test and/or continued monitoring of an abnormal value are not considered an intervention. In addition, repeated or additional noninvasive testing for verification, evaluation, or monitoring of an abnormality is not considered an intervention
- If abnormal laboratory values or ECG findings are the results of pathology for which there is an overall diagnosis (e.g., increased creatinine in renal failure), the diagnosis only should be reported appropriately as an AE

Pre-existing conditions:

- Pre-existing conditions (present at the time of signing of the ICF) are considered concurrent medical conditions and should NOT be recorded as AEs. Baseline evaluations (e.g., laboratory tests, ECG, X-rays, etc.) should NOT be recorded unless related Study Procedures (Appendix A).
- If a participant has a pre-existing episodic condition (e.g., asthma, epilepsy), any occurrence of an episode should only be captured as an AE if the episodes become more frequent, serious, or severe in nature; that is, Investigators should ensure that the AE term recorded captures the change in the condition from Baseline (e.g., "worsening of...")

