- If a participant has a concurrent degenerative condition (e.g., cataracts, rheumatoid arthritis), worsening of the condition should only be captured as an AE if occurring to a greater extent than that which would be expected. Again, Investigators should ensure that the AE term recorded captures the change in the condition (e.g., "worsening of...")

Worsening of AEs:

- If the participant experiences a worsening or complication of an AE after starting administration of the study medication, the worsening or complication should be recorded appropriately as an AE.
- If the participant experiences a worsening or complication of an AE after any change in study medication, the worsening or complication should be recorded as a new AE.

Changes in severity of AEs /Serious PTEs:

• If the participant experiences changes in the severity of an AE, the event should be captured once, with the maximum severity recorded.

Preplanned surgeries or procedures:

Preplanned procedures (surgeries or therapies) scheduled prior to the signing of the ICF are
not considered AEs. However, if a preplanned procedure is performed early (e.g., as an
emergency) due to a worsening of the pre-existing condition, the worsening of the condition
should be captured appropriately as an AE. Complications resulting from any planned
surgery should be reported as AEs.

Elective surgeries or procedures:

• Elective procedures performed where there is no change in the participant's medical condition should not be recorded as AEs but should be documented in the participant's source documents. Complications resulting from an elective surgery should be reported as AEs.

Overdose:

• Cases of overdose with any medication without manifested side effects are NOT considered AEs, but instead will be documented on an Overdose page of the eCRF. Any manifested side effects will be considered AEs and will be recorded on the AE page of the eCRF.

9.6.3 **SAEs**

An SAE is defined as any untoward medical occurrence that at any dose:

- 1. Results in DEATH
- 2. Is LIFE-THREATENING
 - The term "life threatening" refers to an event in which the participant was at risk of death at the time of the event; it does not refer to an event that hypothetically might have caused death if it were more severe
- 3. Requires inpatient HOSPITALIZATION or prolongation of existing hospitalization
- 4. Results in persistent or significant DISABILITY/INCAPACITY
- 5. Leads to a CONGENITAL ANOMALY/CONGENITAL DISABILITY

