11.1.4 Safety Analysis

11.1.4.1 AEs

All AEs will be coded by system organ class (SOC) and preferred term (PT) using MedDRA. Treatment-emergent AEs with onset occurring within 30 days (onset date − last date of dose +1 ≤30) after study drug administration will be listed and included in the summary tables. Treatment-emergent AEs will be summarized by each CVN424 formulation, if in the fed or fasted state, and CVN424 overall by SOC and PT. The following summary tables will be included in the report: summary of TEAEs and drug-related AEs, relationship of AEs to study drug (related vs. not related), severity of AEs, and related AEs. AEs leading to study drug discontinuation and SAEs will be listed. Data listings will be provided for all AEs, TEAEs, AEs leading to study drug discontinuation, and SAEs. All AEs will be listed.

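### SAP 7.4 defines a TEAE by onset alone and, without declaring it, leaves out the worsening limb of protocol 9.6.1; only AEs that start before the Period 1 dose and worsen after it are affected

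*SAP*

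**What the plan says.** Protocol 9.6.1 gives two routes to a TEAE. The AE begins on or after the first dose, "or an increase in severity or frequency on or after administration of the first dose of trial medication". It sets no end to the window.

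SAP 7.4 keeps only the first route and adds an end: "A TEAE is defined as an AE that is starting at the time of or after study product administration and within 30 days" of the final dose. It summarises TEAEs only; other AEs are listed. On attribution it says: "Each TEAE will be attributed to a treatment based on the onset date and time of the AE", compared with the dosing times.

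Protocol 11.1.4.1 sets the reporting window: "Treatment-emergent AEs with onset occurring within 30 days" (a bracketed formula follows) "after study drug administration will be listed and included in the summary tables". It does not mention worsening.

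Protocol 9.6.2 has two recording lines that bear on this. Under worsening of AEs, a worsening "after starting administration of the study medication, the worsening or complication should be recorded appropriately as an AE". Under changes in severity: "If the participant experiences changes in the severity of an AE, the event should be captured once, with the maximum severity recorded". Protocol 9.6.7 dates an AE from its first signs or symptoms.

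SAP Section 8 declares one departure from the protocol, on screen-failure summaries, and nothing on TEAEs.

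**The concern.** TEAEs are the safety endpoint attached to a secondary objective, and the SAP tabulates nothing else for AEs. A SAP that uses a narrower definition than the protocol, without saying so, leaves a reader of the tables unsure which events were eligible. An AE that was mild before dosing and became worse after it is one that a safety reader would want to see. Under SAP 7.4, whether it reaches a table depends on which line of protocol 9.6.2 the site happened to follow, and the plan does not say which line takes precedence.

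**Working it through.** The plan states no figure to reproduce. The check sets the rules side by side and applies them to a test case.

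**Inputs**
- Dosing on Study Days 0, 14 and 28 (protocol Study Summary and Appendix A).
- AE collection from consent to 14 days after the last dose (protocol 9.7.1.1): 28 + 14 = Study Day 42.
- Screening up to 28 days before randomization (protocol 7.0), so AEs can start before the first dose.
- Window formula in protocol 11.1.4.1 and SAP 7.4: onset − last dose + 1 ≤ 30.
- 32 participants planned, 28 evaluable needed (protocol 11.3).

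**Step 1: where the two definitions can differ**
- AE starting on or after the first dose: a TEAE under 9.6.1 and under SAP 7.4. The 30-day limit removes nothing that is routinely collected, since at the end of collection 42 − 28 + 1 = 15 ≤ 30.
- Condition already present at consent: not an AE under protocol 9.6.2. For episodic conditions that become worse, "Investigators should ensure that the AE term recorded captures the change in the condition from Baseline", and degenerative conditions have a similar instruction. The change is then an AE in its own right.
- AE starting between consent and the Period 1 dose that does not worsen: a TEAE under neither.
- AE starting in that interval that worsens after dosing: the only case left.

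**Step 2: that case under each recording path.** Take onset on Study Day −5 and worsening on Study Day 1. A 1 means counted as a TEAE.

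| How it is recorded | Protocol 9.6.1 | Protocol 11.1.4.1, read literally | SAP 7.4 |
|---|---|---|---|
| One record, start Day −5, maximum severity | 1 | 0 | 0 |
| Worsening as its own record, start Day 1 | 1 | 1 | 1 |

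The formula does not exclude the first row: −5 − 28 + 1 = −32 ≤ 30. It is excluded by the requirement in SAP 7.4 and 11.1.4.1 that onset follow study drug. In the second row, 1 − 28 + 1 = −26 ≤ 30 and onset is post-dose, so all three count it.

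**Step 3: can the first row be repaired at analysis?** Protocol 9.7.1.2 lists one start and stop date and time, one severity and one frequency per event. No date of worsening is listed. Adding the missing limb to SAP 7.4 would therefore not be enough to recover a single-record event; the recording rule has to change with it.

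**Step 4: size.** One affected participant moves the incidence of one preferred term under one treatment by at most 1/32 = 3.1 percentage points, or 1/28 = 3.6 points if only 28 receive that treatment. The step is 0 if that participant has another TEAE of the same term under that treatment.

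**The case against.** The strongest reply is that the protocol already has a specific rule for this case. The line on worsening addresses an AE that becomes worse after study medication starts, while the captured-once line is general and does not mention dosing. If the specific line governs, the worsening has its own post-dose record and SAP 7.4 counts it. That is the more natural reading. It does not close the gap, because both lines stand in 9.6.2, neither is given precedence, and the first-symptom start date makes the single-record path an easy one to follow.

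It can also be said that protocol 11.1 leaves details of analysis variables to the SAP, and that SAP Section 1 sends changes to the CSR. Both are true. But leaving out one of two limbs is a change rather than a detail, and Section 8 is where the SAP lists its changes.

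Four stronger readings are tempting, and the documents do not support them:
- That the protocol holds two rival definitions. Section 11.1.4.1 starts from a term already defined in 9.6.1 and sets a reporting window. Its onset wording is loose, but the firm conflict is between 9.6.1 and SAP 7.4.
- That all worsening AEs disappear from the tables. Only those kept as one record with a pre-dose start do.
- That single-record events can never be recovered. The eCRF is not among the documents. The list in 9.7.1.2 shows no date of worsening, and no more than that can be said.
- That treatment comparisons are biased. The affected events begin before any study drug, nothing in the plan ties the recording choice to treatment, and 9.6.2 separately asks for a new AE when an event worsens after a change in study medication.

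**Conclusion.** The point holds and is minor. SAP 7.4 is narrower than protocol 9.6.1, and Section 8 does not say so. The consequence is confined to AEs that start between consent and the Period 1 dose, worsen after dosing and are kept as one record. Each such participant changes a treatment's incidence of a preferred term by at most 3.1 percentage points with 32 dosed. That is a ceiling for one participant, not an expected effect. In healthy volunteers the number may be zero. The event remains in the by-participant AE listing, and PK conclusions are unaffected.

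This rests on two assumptions: that the site may follow either line of 9.6.2, and that the eCRF records no more than the fields in 9.7.1.2.

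**What to change.** 1. Recording. State by eCRF completion note or note to file that, for an AE with onset before the Period 1 dose, the worsening line of 9.6.2 takes precedence over the captured-once line. The post-dose worsening is entered as its own record, with the date and time of worsening as its start. Only that record counts as the TEAE, and the pre-dose record stays in the listing, so nothing is counted twice.
2. Definition. Add to SAP 7.4 the limb for an AE that increases in severity or frequency on or after the first dose. Keep the 30-day limit. Attribution needs no new rule: the new record's onset assigns it to the last treatment given before the worsening. Word protocol 11.1.4.1 to match.
3. Fallback. The statistical outputs filed with the SAP are dated 8 March 2023, so data collection may no longer be open to change. In that case, declare in SAP Section 8 or the CSR that the TEAE tables use an onset-only definition, narrower than 9.6.1.

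The cost is one completion note and a clause in each of two sections, or a single declaring line under the fallback. The downside of changing the recording is a few more AE records and a slightly higher TEAE count.

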7.5 Clinical Laboratory Tests (Serum Chemistry, Hematology, Coagulation and Urinalysis)

Clinical laboratory tests will be measured at the following time points:

Clinical Laboratory Panels	Time Point		
	Period	CRF/Listing Day and Hour	Table
	Screening		NA
Serum Chemistry,	1, 2, 3	Day -1 Hour -26.25, -25.75	NA
Hematology, Coagulation,		Day 1 Hour -2.00, -1.75	Baseline
Urinalysis		Day 2 Hour 23.77*^	Day 2^
		Day 3 Hour 48.00^	Day 3 [^]
		Day 5 Hour 95.77*, 96.00	Day 5

Time points in the CRF/Listing column are approximated/based on the blank CRF and it should be noted that the data listings will reflect the data found in the final participant CRFs.

If applicable, an early termination assessment will be performed.

NA = Not applicable; *Period 2 is at X.75 instead of X.77, ^Urinalysis is not collected on Days 2 and 3.

Clinical laboratory results will be presented as extracted from the clinical laboratory database. Out-of-reference range flags will be recorded as follows: high (H) and low (L) for numerical results and did-not-match (*) for categorical results.

Out-of-reference range values and corresponding recheck results will be listed. Out-of-range clinical laboratory values which are deemed clinically significant will be entered, listed, and summarized with the AEs.

Clinically significant labs would be denoted as AEs and listed/summarized as such.

For all numeric laboratory values, descriptive statistics will be presented for each laboratory test by assessment time point and treatment. Change from baseline will be summarized in a

similar manner. In line with the protocol, an overall column will also be included for these descriptive statistics for which the baseline will still be the treatment specific baselines. For all numeric laboratory tests, the mean value calculated for each assessment time point and treatment will be compared to the reference range and flagged if outside of the reference range (* if above the reference range and ^ if below the reference range). In the event there is more than one reference range for a laboratory test, the comparison will be made against the lowest of the lower ranges and the highest of the higher ranges.

For each laboratory test, a shift table will be developed to compare the frequency of the results at baseline (above reference range, within reference range, or below reference range) with the respective postdose results by treatment. For urinally is tests, the categories are within reference range and outside reference range.

7.6 Vital Signs

Vital signs will be measured at the following time points:

Parameter	Time Point		
	Period	CRF/Listing Day and Hour	Table
	Screening		NA
	1, 2, 3	Day -1 Hour -24.83	NA
Orthostatic [Blood		Day 1 Hour -0.83	Baseline
Pressure and Heart Rate].		Day 1 Hour 1.63*	Hour 1.5*
Respiration, Temperature		Day 2 Hour 24.08	Day 2
		Day 3 Hour 48.08	Day 3
		Day 4 Hour 72.08	Day 4
		Day 5 Hour 96.08	Day 5
Weight	Screening		NA (summarized in
Weight			demographics)
	3	Day 5 Hour 96.25	NA

Time points in the CRF/Listing column are approximated/based on the blank CRF and it should be noted that the data listing will reflect the data found in the final participant CRFs.

Heart rate is labeled as pulse in the CRF.

If applicable, an early termination assessment will be performed.

NA = Not applicable

Per protocol, the supine measurements are sometimes collected in triplicate. In these cases, the averaged (to the nearest tenth) of the supine measurements, collected within 15-minute window prior to the standing measurements will be used in all summaries. In the case that there are more than 3 collected in the 15-minute window, the 3 records closet to the standing will be used in the average. For time points when averages are derived, the averages will be summarized instead of the individual measurements.

Descriptive statistics will be presented for vital signs measurements by assessment time point and treatment. Change from baseline will be summarized in a similar manner. An across

^{*}Periods 2 and 3 only

summary treatment column will be included but it should be noted that the change from baseline will be treatment specific change.

Orthostatic change will be calculated for blood pressure and heart rate at the time points listed by subtracting the supine (or average supine, as applicable) measurement from the standing measurement (i.e. orthostatic change = standing measurement – supine measurement). Descriptive statistics will be presented for each orthostatic vital sign parameter by assessment time point and treatment. Change from baseline will be summarized in a similar manner. Similar to the vital sign summaries, an overall column will be included. Baseline will typically be the orthostatic change result obtained prior to dosing on Day 1 of each period. Any standing vital sign measurement collected more than 15 minutes after the corresponding supine (or average, as applicable) measurement will be excluded from analysis. At postdose time points, the first complete orthostatic assessment (i.e. assessment with supine result(s) and corresponding standing result) will be used during analysis. If the first complete orthostatic assessment is not the original assessment at a given postdose time point (e.g., original assessment has supine result(s) and no corresponding standing result), the first complete orthostatic assessment will only be used during analysis if this assessment starts within 30 minutes of the original incomplete assessment. Other postdose unscheduled and early termination measurements will not be included in orthostatic vital sign summaries.

Abnormal vital signs which are deemed clinically significant will be entered, listed, and summarized with the AEs.

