16.1 Study Information

16.1.1 Protocol and Protocol Amendments

Note to File 21 October 2022

Note to File 20 October 2022

Note To File 30 September 2022

Final Protocol 30 August 2022

cerevance

NOTE TO FILE

To: Cerevance 424-102 Study Trial Master File

From: Consultant to Cerevance

Date: 21Oct2022

Study: CVN424-102

Re: Protocol Clarifications

The following are clarifications for the CVN424-102 protocol version 1.0 dated 30Aug2022.

- 9.1.5 Vital Sign Procedure
 - Clarifying that respiration rate is not needed in triplicate
 - Clarifying that the triplicate measurements at the "initial post-dose" timepoint are to be collected from 1-3 hours post administration of the study drug
 - Subsequent post-dose measurements (i.e., 24-, 48-, 72-, and 96- hours) are not needed in triplicate

Signed,

Consultant
Cerevance

NOTE TO FILE

To: Cerevance 424-102 Study Trial Master File

From: Consultant to Cerevance

Date: 20Oct2022

Study: CVN424-102

Re: Protocol Clarifications

The following are clarifications for the CVN424-102 protocol version 1.0 dated 30Aug2022.

The language in section 9.7.3 Reporting of Abnormal LFT, is to be updated as follows below. The rationale for the change is to better align with section 7.4 Criteria for Discontinuation or Withdrawal of a Participant.

Existing language:

If a participant is noted to have ALT or AST elevated >3 ×ULN on 2 consecutive occasions, the abnormality should be recorded as an AE at the discretion of the PI. In addition, an LFT increases eCRF must be completed by providing additional information on relevant recent history, risk factors, clinical signs and symptoms, and results of any additional diagnostic tests performed.

If a participant is noted to have ALT or AST >3 ×ULN and total bilirubin >2 ×ULN for which an alternative etiology has not been identified, the event should be recorded as an SAE and reported as per Section 9.7.2. The Investigator must contact the Medical Monitor to discuss the relevant participant details and possible alternative etiologies, such as acute viral hepatitis A or B or other acute liver disease or medical history/concurrent medical conditions. Follow up laboratory tests will be at the discretion of the Investigator.

To be replaced with:

If a participant is noted to have ALT or AST elevated >2 ×ULN at any point, the abnormality should be recorded as an AE.

If a participant is noted to have

[figure not shown]

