CVN424 is a potent and selective inverse agonist of GPR6. Two studies have been completed with CVN424 in human participants.

A first-in-human safety study of CVN424 in 64 healthy volunteers has been completed (NCT03657030); the study findings are summarized in the Investigator's Brochure. In brief, CVN424 was safe and well tolerated when administered to healthy participants as a single oral dose of between 1 milligram (mg) and 225 mg or when administered as 7 daily oral doses of between 25 mg and 150 mg. Study drug-related adverse events (AEs) were reported by 2 of 40 participants (5.0%) overall in the single-dose cohorts (feeling hot; headache). Study drug-related AEs were reported by 2 of 24 participants (8.3%) overall in the multiple-dose cohorts (dysphagia; chills). With one exception, all AEs were mild in severity; dysphagia of moderate severity led to treatment discontinuation in one participant after their third daily dose (75 mg). There were no severe or serious AEs, and all AEs resolved by the end of the study. Administration of the first dose of CVN424 was associated with an elevation in group mean and median body temperature.

Page 16 of 64 30 Aug 2022

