9.1.5 Vital Sign Procedure

Orthostatic vital signs will be measured after the participant has been at rest in a supine position for at least 3 minutes. Vital signs include blood pressure (BP), pulse rate, respiration rate, and body temperature. Triplicate measurements will be taken at pre-dose, initial post-dose, and final study assessment to ensure accuracy unless values are unexpected and additional measurements are clinically indicated for confirmation. Additionally, abnormal or unexpected measurements are to be rechecked manually.

Vital signs should be measured at the same time (+/- 1 hour) of the day across visits if possible. When vital signs are scheduled at the same time as blood draws, the blood draw will take priority, and vital signs will be obtained within approximately 15 minutes before or after the scheduled blood draw.

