Appendix A: Schedule of Study Procedures

Overall Study Day #	-28 to -2	-1	0	1-4	5-12	13	14	15-18	19-26	27	28	29-32	33 +/- 2
Period				1			2				3	3	
Day		0	1	2-5	6-13	14	1	2-5	6-13	14	1	2-5	15 +/- 2
					Washo	ut			Washout				
			Inpati	ent	ent		Inpatient				Inpatient		
	Screening	Check- in	Dosing			Check-in	Dosing Day			Check-in	Dosing		Follow- Up/ET¹
Informed Consent	X												
Inclusion/Exclusion Criteria	X												
Review ICF and I/E	X	X				X				X			
Demographics and Medical History	X												
Randomization ²		X											
Concomitant medications	X	X	X	X		X	X	X		X	X	X	X
Participant Admission to CRU		X				X				X			
Vital signs ³	X	X	X	X		X	X	X		X	X	X	X
Weight, height, and BMI ⁴	X												X
Urinalysis ⁵	X		X	X			X	X			X	X	X
Urine Drug Screen	X	X				X	_			X	_	_	
Cotinine Screen		X				X				X			

¹ Assessments to be completed on final in-patient day and will be repeated if AE requires in-person follow-up

² Once eligibility has been confirmed by Screening assessments ³ Assessments to include HR, BP, and temperature

⁴ Height only at screening ⁵ Part of safety assessments (Pre and 24h post-dose)

Page 62 of 64 30 Aug 2022

Physical Examination ⁶	X		X			X			X		X
Hepatitis panel and HIV antibody test	X										
Clinical laboratory tests ⁷	X	X	X	X		X	X		X	X	X
Pregnancy Test ⁸	X	X		X	X		X	X			X
FSH ⁹	X										
C-SSRS ¹⁰	X	X		X	X	X	X	X	X	X	X
ECG ¹¹	X		X			X			X		X
PK Blood Collection ¹²			X	X		X	X		X	X	
PK Urine ¹³			X	X		X	X		X	X	
Overnight Fasting		X ¹⁴			X^{15}			X^{16}			
CVN424 Dosing ¹⁷			X			X			X		
AE Assessment		X	X	X	X	X	X	X	X	X	X

⁶ Full PE at Screening, Medical Assessment pre-dose (within 24 hours prior to dosing) and 24-hours post-dose

⁷ Pre and Post dose Safety Labs, standard hematology with WBC differential, CRP, coagulation tests, lipase, amylase, albumin, and calcium. Predose labs do not need to be reviewed prior to dosing. Post dose to be done at 48 hours and EOT. Unscheduled as clinically indicated.

⁸ Serum pregnancy test at Screening and urine pregnancy test at subsequent discharge and check-ins

⁹ FSH level will be obtained on post-menopausal women (defined as continuous amenorrhea of at least 2 years and not surgically sterile)

¹⁰ Screening, Check-in, 24 and 96-hour post dose

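### SAP 7.6 limits the only vital-sign set before 24 hours post-dose to Periods 2 and 3, so the Hour 1.5 summary contains none of the 32 first exposures

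*SAP*

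**What the plan says.** The time-point table in SAP 7.6 gives a baseline at Hour -0.83, a post-dose set at "Day 1 Hour 1.63" (labelled Hour 1.5 in tables), and then nothing until Hour 24.08 on Day 2. The Hour 1.63 row is starred, and the star reads "Periods 2 and 3 only". No reason is given. SAP Section 8 lists only the screen-failure summaries as a change from the protocol. The SAP adds that "Time points in the CRF/Listing column are approximated/based on the blank CRF".

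Protocol 9.1.5 states: "Triplicate measurements will be taken at pre-dose, initial post-dose, and final study assessment to ensure accuracy". The note to file of 21 October 2022 says that the initial post-dose measurements "are to be collected from 1-3 hours post administration of the study drug", and then: "Subsequent post-dose measurements (i.e., 24-, 48-, 72-, and 96- hours) are not needed in triplicate". Neither text names a period. Appendix A marks vital signs on the dosing day of all three periods, with the footnote "Assessments to include HR, BP, and temperature". That is consistent with an early set in every period but gives no clock time.

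Protocol 4.1 supplies the background: "Administration of the first dose of CVN424 was associated with an elevation in group mean and median body temperature". The rise was seen at 1 hour, was larger by 6 hours and was gone by 24 hours. Standing heart rate showed a trend with a similar time course. In the multiple-dose cohorts, these elevations followed only the first dose.

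**The concern.** Each participant takes a first dose in Period 1. That is the exposure for which the protocol's own background describes an acute change in temperature and standing heart rate, and it is the one that SAP 7.6 leaves without an early reading. The next planned reading comes at 24.08 hours, by which time the earlier study had seen values return to baseline.

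The other Period 1 information is limited. The ECG at about Hour 2.75 gives heart rate, but Protocol 9.1.8 has it recorded supine, so it says nothing about standing heart rate, temperature or blood pressure. SAP 7.6 sends clinically significant vital signs to the AE summaries, but only a reading that was taken can be judged. SAP Section 7 keeps unscheduled readings out of the post-baseline summaries.

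Safety is a secondary objective. A reader of Table 14.3.5.9 could take a flat Hour 1.5 row as evidence against an acute effect, when it contains only second and third exposures. The restriction is disclosed under the SAP's table, so nothing is concealed. The fault is that it is unexplained and conflicts with the protocol.

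**Working it through.** **Inputs.** Sequence sizes and order are from SAP Section 3 and the sequence labels in the disposition shell: ABC 5, BCA 6, CAB 5, ACB 5, BAC 5, CBA 6. There is one dose per period. Times are from SAP 7.6.

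**Planned total.** 5 + 6 + 5 + 5 + 5 + 6 = 32, which matches the stated enrolment. Three periods give 3 × 32 = 96 exposures.

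**Exposures by period**, if all 32 complete:

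| | A (suspension fasted) | B (tablet fasted) | C (tablet fed) | Total |
|---|---|---|---|---|
| Period 1 | 5+5 = 10 | 6+5 = 11 | 5+6 = 11 | 32 |
| Period 2 | 5+5 = 10 | 5+6 = 11 | 6+5 = 11 | 32 |
| Period 3 | 6+6 = 12 | 5+5 = 10 | 5+5 = 10 | 32 |
| Periods 2+3 | 22 (68.8%) | 21 (65.6%) | 21 (65.6%) | 64 (66.7%) |

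The Hour 1.5 row therefore holds at most 64 of 96 exposures. The 32 left out are exactly the first exposures. Dropouts can lower the 64 but cannot add a first exposure.

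**Period 1 gap.** 24.08 − (−0.83) = 24.91 hours.

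**What the row can show.** Assume later exposures produce a fraction f of the first-dose mean shift. The documents give no value, so f runs from 0 to 1. The current row shows f of the shift. If Period 1 were added and pooled, first exposures would be 10/32 = 31.25% of cell A and 11/32 = 34.38% of cells B and C, so the row would show 0.3125 + 0.6875f (A) or 0.3438 + 0.6562f (B, C).

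| f | Current row | Period 1 pooled, A | Period 1 pooled, B and C |
|---|---|---|---|
| 0 | 0% | 31% | 34% |
| 0.5 | 50% | 66% | 67% |
| 1 | 100% | 100% | 100% |

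Pooling alone would dilute a first-dose-only effect to about a third, so Period 1 needs its own display.

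**Reading the texts together.** If the initial post-dose set means one per period, Period 1 is included. If it means one per study, Period 1 is where it falls. Neither reading drops Period 1. The note treats 24 to 96 hours as subsequent, so under it the Hour 24.08 set cannot stand in. Nor does the star look like a clock-time variant: SAP 7.5 marks such a variant by giving the alternative time, whereas SAP 7.6 says only and gives no Period 1 time.

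**The case against.** The conflict and the counts are not in dispute. The case against concerns origin, timing and weight.

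- **Origin.** An SAP does not control collection, and this one says its times follow the blank CRF. The gap may lie in the CRF. This stands, and the fix must cover both.
- **Timing.** Before the note, 9.1.5 gave no clock time, so excluding the 24-hour set as the initial one rests on the note. A set missing only in Period 1 is what a mid-study clarification could produce. The documents give no dosing dates, so this is possible but unconfirmed. It would be a reason to state, and none is stated.
- **Late remedy.** SAP 7.7 describes the Day 5 ECG in the past tense and the appended outputs are dated 8 March 2023, so Period 1 may have been over. Collection would then be impossible and only disclosure would remain.
- **First-dose premise.** The first-dose-only pattern came from daily dosing. Here doses are 14 days apart, which is 14 × 24 / 33 = 10.2 half-lives, so Periods 2 and 3 are close to fresh single doses pharmacokinetically. Phase 2 saw pulse and blood-pressure rises on Day 8 as well as Day 1, though Day 8 was also the dose step-up in one arm. This leaves it open whether Periods 2 and 3 can substitute for Period 1. It does not show that they can.
- **Weight.** The earlier trends were judged not clinically significant, the listed safety endpoints are TEAEs and discontinuations, AEs are assessed on every dosing day, and 9.1.5 allows extra measurements when clinically indicated. No document claims that a first-dose effect is absent. This limits the severity but does not remove the conflict.

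**Conclusion.** The concern holds. SAP 7.6 as written conflicts with Protocol 9.1.5 and the 21 October 2022 note. The Hour 1.5 summary would contain at most 64 of 96 exposures and 0 of 32 first exposures, with a 24.91-hour gap in Period 1 for temperature, blood pressure and standing heart rate.

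The counts assume full enrolment and completion. How much signal is lost depends on f, which is unknown: all of a first-dose-only effect at f = 0, none at f = 1. The row therefore cannot support absence of an acute first-dose effect. This should be corrected, but it affects only a descriptive safety summary and leaves the primary bioavailability analysis untouched. Whether the gap began in the CRF, and whether Period 1 came before the note, cannot be settled from the documents.

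**What to change.** Reconcile SAP 7.6 and the CRF with Protocol 9.1.5 and the 21 October 2022 note, so that the Day 1 set at 1 to 3 hours is collected and summarised in Period 1 too. At Hour 1.5, show Period 1 apart from Periods 2 and 3. The cost is one vital-sign set per participant, which the protocol already requires. Participants are confined and already have an ECG at Hours 2.75 to 2.78 in Period 1, inside the same window.

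If Period 1 readings do not exist:

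- state this and the reason in SAP Section 8 or the CSR;
- carry the period footnote onto Table 14.3.5.9;
- state that the Hour 1.5 row contains no first-exposure data and cannot support absence of an acute first-dose effect.

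That costs an explanatory statement and a table footnote. It discloses the gap but does not fill it.

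Neither route supplies a reading near 6 hours, where the earlier study saw larger changes and where no period has a planned set. Any conclusion should be limited to the 1 to 3 hour window.
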